Using Gum Arabic for Cancer Patients to Protect From Oral Mucositis Caused by Chemotherapy: An Experimental Study

NCT ID not yet assigned

15/11/2017

Study protocol

Background

Investigate agents which can be used to prevent or treat chemotherapy-induced oral mucositis is a primary concern for clinicians and researchers. The synthesis pharmacological drugs are costly and associated with much side effects resulting in patient non-compliance. So, there is a need to find alternative therapies especially from natural sources as these are cost effective and have no or minimal side effects. In this regard, Gum Arabic is very convenient since this polymer is readily available on nature and does not require any further complex method of purification. Also it is a safe material for biological applications.

Objective of study

The purpose of this research was to investigate the effect of Gum Arabic to prevent chemotherapy-induced oral mucositis in cancer patients.

Inclusion criteria

Patients whom well diagnosed with cancer in any stage were eligible for enrolment if chemotherapy is a part of the treatment plan.

Exclusion criteria

Patients will be excluded if recently received chemotherapy or radiotherapy, presence of oral mucositis or periodontitis, or there is evidence of any systemic diseases.

Dose, preparation and administration of gum arabic

The daily dose of Gum Arabic will be divided in 30 grams sachet, the content of sachet will dissolve once in 100 ml purified water to form solution, and consuming

in six divided doses. Patient will provide by measuring cap to using 20-ml every two hours as mouthwash for a minute then swallow.

The total number of sachets are 42 for a period of six weeks; each patient will give 21 sachet of Gum Arabic at the first day of chemotherapy treatment to be used during the next three weeks of the treatment period, then the remain quantity (21 sachets) will provide for the next three weeks.

Modification on the preparation and administration

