Because frequent use during the day (six times; each 2 hours) and high viscosity of gum arabic solution, which lead to withdrawn some patients after were enrolled in this study. Researcher was tried to solve this problem at two sides; firstly, by increasing the quantity of purified water as solvent for Gum Arabic to 250 milliliters instead of 100 milliliters to reduce viscosity of solution. On the other hand, patient was informed to use this quantity of solution twice daily; half at 9 morning and the remaining half at 9 evening to decrease frequent uses.

Oral mucositis assessment:

Based on a combination of subjective, objective and functional outcomes, using World Health Organization Oral Toxicity Scale (WHO Score): subjective – soreness as described by the patient, objective – presence of erythema and ulcerations, and functional – ability to eat solids, liquids or nothing by mouth

Assessment gum Arabic effect

For each participant data of oral mucositis will be start after getting ethical committee permission & permission from Radiation and Isotopes Center of Khartoum (RICK) authority. Informed consent also will be taken from study participants.

Data will gather via data collection sheet which composed of two sections; that will fill through six weeks of patient follow up. The first part for assessment patient regarding oral mucositis after chemotherapy by weekly telephone call for patient based on ready-scheduled appointments. The second part contain a basic information and characteristics of patient, which will record by researcher during the first day at first cycle of chemotherapy. In addition, there is meeting with patients by researcher in chemotherapy rooms when the participant return to the next cycle of chemotherapy either weekly, bi-weekly or every three weeks, according to treatment regimen.

When the researcher is contacted with the patient either by telephone call or when meeting participant in the hospital during the next chemotherapy cycle; there will be specific questions directed by the researcher to be answered by the patient regarding oral mucositis. Those questions will be summarized as follow: 1. Does the oral mucositis was occurred during this week? 2. If Yes. Is there was soreness, erythema, ulcers in mouth of participant? 3. The day that oral mucositis was started and eliminated? 4. If the patient belong to study group; Is Gum Arabic still used regularly? Six weeks for each participant from starting therapy.

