Cessation of trial therapy

No stop for recruiting the participants to study group until the planned number was completed, but there was a period of three weeks the new recruitment was suspended to separate study group from control group in try to reduce the bias (reduce the confounding) between the two groups and give a chance to follow up the study group patients. By August 2016 we stopped participants recruitment and follow up; since the sample size proposed and follow up planned was completed.

Statistical analysis

The collected data were arranged, coded, tabulated, and introduced to a personal computer using Statistical Package for Social Science (IBM SPSS Statistics 20.lnk). P. values equal or less than 0.05 was considered significant. The data of 332 patients who completed this study were documented and reviewed to give a qualitative analysis of the frequencies. The descriptions were based on the data that documented from personal file of patient in designed sheet prepared by the researcher. Data were presented and suitable analysis was done according to the type of data obtained for each parameter. All numeric variables were expressed at 95% confidence intervals. Student t-test was used to assess the statistical significance of the difference between means of the two groups.

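### The p ≤ 0.05 rule does not carry a 5% error rate for a conclusion on prevention, because nothing in the document shows an outcome or test fixed before the data were reviewed

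*Combined protocol and SAP*

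**What the plan says.** The title block of the combined protocol and SAP carries one date, 15/11/2017, and notes that no NCT number had yet been assigned. The objective is to "investigate the effect of Gum Arabic to prevent chemotherapy-induced oral mucositis in cancer patients".

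Under Cessation of trial therapy: "By August 2016 we stopped participants recruitment and follow up". Under Statistical analysis, in the past tense: "The data of 332 patients who completed this study were documented and reviewed".

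On method, the same section gives three statements:

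- The choice of analysis: "suitable analysis was done according to the type of data obtained for each parameter".
- The decision rule: "P. values equal or less than 0.05 was considered significant".
- The only named test: "Student t-test was used to assess the statistical significance of the difference between means of the two groups".

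Under Assessment gum Arabic effect, the outcome questions put to patients begin with "Does the oral mucositis was occurred during this week". If the answer is yes, they continue with "Is there was soreness, erythema, ulcers in mouth of participant" and with the days on which the mucositis began and cleared.

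**The concern.** A 0.05 threshold limits false positives to 1 in 20 for one comparison, chosen without sight of its result. Here the text was written when the data were in hand and reviewed. The objective concerns prevention, which is most directly a question of whether mucositis occurred, yet no test is given for occurrence. The one named test compares means, and the document does not say of which variable. Several outcomes were collected, none is ranked above the others, and each may be declared significant on its own p-value.

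At stake is how a positive result may be read. A reader who meets a p-value below 0.05 in a study with a document headed as a protocol will take the comparison as planned and its error rate as 5%. This document supports neither assumption.

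**Working it through.** **The plan's own figure.** The only number in the statistical section, apart from the significance and confidence levels, is 332. It is a count of completers. No effect size, event rate, standard deviation or power is given, so it cannot be reproduced as a sample size, and it does not show which outcome the study was sized for.

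**Step 1: timing.** Follow-up stopped by August 2016, with no day given. The document date is 15 November 2017.

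- From 31 August 2016: 365 days to 31 August 2017, plus 30 + 31 + 15 = 76 days, gives 441 days. 441 / 30.4375 = 14.5 months.
- From 1 August 2016: 441 + 30 = 471 days. 471 / 30.4375 = 15.5 months.

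The text could mean a stop before 1 August, so 15.5 months is not a ceiling. The lower bound of 14 months holds on any reading.

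**Step 2: what the document fixes.**

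| Element | Stated? |
|---|---|
| Primary outcome | No |
| Test for occurrence of mucositis (yes/no) | No |
| Test for means | Student t-test, variable not named |
| Threshold | 0.05, sidedness not stated |
| Multiplicity rule | No |
| Citation of an earlier dated plan | No |

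**Step 3: size of the effect on the error rate.** The weekly questions yield six outcome items: occurrence, soreness, erythema, ulcers, start day and end day. Suppose the product has no effect and each item is tested once at 0.05.

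If the tests are independent, the chance of at least one p ≤ 0.05 is 1 − (1 − 0.05)^k:

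- k = 6: 1 − 0.95^6 = 0.265
- k = 3: 1 − 0.95^3 = 0.143

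The items are related, so independence overstates the figure for a given k. With equally correlated normal test statistics, two-sided tests at 0.05 and 400,000 simulated draws:

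| Assumed correlation | k = 3 | k = 6 |
|---|---|---|
| 0.3 | 13.5% | 24.2% |
| 0.5 | 12.5% | 20.7% |
| 0.8 | 9.8% | 13.9% |

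Even with three strongly correlated items, the chance is about twice the nominal 5%.

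**The case against.** Four arguments on the other side deserve weight.

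- **The wording on choice of analysis.** Its ordinary meaning is that the test was matched to the measurement scale, such as a t-test for numeric variables. A reader might infer that tests were chosen by looking at results. The document does not say so, and that inference should be dropped. Scale, however, settles the kind of test; it does not settle which outcome carries the conclusion.
- **The date.** A reader might infer that the analysis was first planned in November 2017. The missing NCT number suggests a text prepared for registration. The future tense in the methods, and the references to a planned number of participants and a proposed sample size, suggest an earlier plan. This stands: the date shows when this version was written, not when decisions were made. Yet no earlier plan is cited, and a proposed sample size does not show that an outcome or test was fixed.
- **No confirmatory claim is made.** This is true. The document says it will investigate an effect and does not use the word confirmatory. The point therefore limits interpretation; it is not an internal contradiction.
- **The size is illustrative.** This is also true. A reader might go further, adding weekly WHO grades and week-by-week t-tests to reach a higher figure. The document names the WHO scale, but the weekly questions as summarised include no item on ability to eat, and weekly tests are never mentioned. That larger figure is not established.

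**Conclusion.** The point holds as a limit on what may be concluded. This version postdates the end of follow-up by at least 14 months, was written with the data reviewed, and shows no outcome or test fixed earlier. A p-value at or below 0.05 from it therefore does not carry a 5% error rate for a conclusion on prevention.

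For six items the illustrative false-positive chance is 26.5% if independent and about 14 to 24% at correlations of 0.8 to 0.3. These figures assume that all six items are tested once each, two-sided, and that any one result at p ≤ 0.05 would be read as support for prevention. The correlations are assumed, since the documents give none. The calculation concerns multiple testing only; it does not address whether the two groups are comparable.

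The documents do not support a finding that the analysis was driven by results. A dated version from before recruitment that fixed an outcome and test would restore the usual reading for that one analysis.

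**What to change.** In Statistical analysis:

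1. State that this version is dated 15/11/2017, after follow-up was complete and the data were reviewed. Cite any version approved before recruitment.
2. If that version fixed an outcome and a test, report that analysis as the only pre-specified one and label all others post hoc.
3. If it did not, or no such version exists, replace the sentence declaring significance at 0.05. Say instead that p-values are descriptive and that the conclusion is a hypothesis-generating association.
4. In either case, report every outcome on the collection sheet with its estimate and 95% confidence interval, whatever its p-value.

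Naming a primary outcome now would not do the same job, because the choice would be made after the data had been reviewed.

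The cost is some wording and one more results table, with no new data. The downside is a weaker claim in the report unless an earlier version supports a stronger one.

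### The groups appear to have been recruited in separate periods without randomisation, yet the only named group comparison is an unadjusted t-test, and no outcome is named as the main one

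*Combined protocol and SAP*

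**What the plan says.** The Objective of study section gives the aim as preventing chemotherapy-induced oral mucositis. No outcome, time point or summary measure is called primary.

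The Oral mucositis assessment section describes one assessment on the WHO scale, combining soreness, visible signs and "ability to eat solids, liquids or nothing by mouth". Under Assessment gum Arabic effect, the researcher asks at each contact over six weeks "Does the oral mucositis was occurred during this week". Soreness, erythema and ulcers are asked about only after a 'yes', and a further question asks for "The day that oral mucositis was started and eliminated". The data sheet also holds "basic information and characteristics of patient, which will record by researcher during the first day at first cycle of chemotherapy". Patients are met in person "when the participant return to the next cycle of chemotherapy either weekly, bi-weekly or every three weeks, according to treatment regimen".

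The Statistical analysis section sets a threshold of p at or below 0.05 and ties it to no outcome. It promises analysis suited to the type of data, and names one group comparison: "Student t-test was used to assess the statistical significance of the difference between means of the two groups". It mentions no variable, covariate or multiplicity rule. The data are those of 332 patients who completed the study; the split by group is not given.

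Under Cessation of trial therapy, new recruitment was suspended for three weeks "to separate study group from control group in try to reduce the bias (reduce the confounding) between the two groups". Randomisation is not described anywhere.

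**The concern.** A recruitment pause keeps two groups apart in time; it does not make them alike. The Inclusion criteria admit any cancer at any stage, and regimens ran on three different cycle intervals. If the mix of cancers, stages or regimens shifted between the two periods, an unadjusted comparison carries that shift into the estimated effect. It could create a benefit, create a harm or hide a real benefit. The plan has day-one characteristics in hand and does not say that they are used.

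The second issue is smaller. Because no outcome is fixed as the answer to the prevention question, a result at p of 0.05 or less on occurrence, WHO score or duration could be put forward as that answer.

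**Working it through.** The documents give no sample size calculation, group split, event rate or effect size, so no figure of theirs can be reproduced here. Apart from the total of 332, the 42 days of follow-up and the 0.05 threshold, every input below is an assumption. The tests are taken as two-sided.

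**1. Exposure to chemotherapy.** Cycles begun in 42 days, counting day one: weekly 6, bi-weekly 3, three-weekly 2. Cycle interval is thus a plausible source of imbalance.

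**2. Bias from one factor, no true effect.** Assume 166 per group (332/2) and one recorded risk factor in 40% of gum arabic and 60% of control patients.

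- Bias in the risk difference = (0.40 − 0.60) × (risk with factor − risk without).
- Risks 0.50 and 0.30: gum arabic 0.4×0.50 + 0.6×0.30 = 0.38; control 0.6×0.50 + 0.4×0.30 = 0.42; difference −0.04.
- Risks 0.60 and 0.20: 0.36 v 0.44; difference −0.08.

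**3. How often that is called a benefit.** Pooled SE = √(2 × 0.40 × 0.60 / 166) = 0.0538, so the critical difference is 1.96 × 0.0538 = 0.1054.

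- First case: unpooled SE = √((0.38×0.62 + 0.42×0.58)/166) = 0.0537; Φ((0.04 − 0.1054)/0.0537) = Φ(−1.22) = 0.11.
- Second case: unpooled SE = √((0.36×0.64 + 0.44×0.56)/166) = 0.0536; Φ((0.08 − 0.1054)/0.0536) = Φ(−0.47) = 0.32.

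Simulation (40,000 runs) gives 0.112 and 0.314, against a nominal 0.025. After stratum standardisation on the factor, the rate is 0.024 to 0.029 in each direction.

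| Variation | Unadjusted, risks 50%/30% | Unadjusted, risks 60%/20% |
|---|---|---|
| Factor 45% v 55%, benefit called | 5% | 11% |
| Factor 60% v 40%, harm called | 11% | 32% |
| Factor 40% v 60%, 232 v 100 patients, benefit called | 10% | 28% |

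**4. A real effect hidden.** Assume a true risk ratio of 0.625 (40% to 25% in balanced groups) and the factor in 60% of gum arabic v 40% of control patients. In the first risk setting the unadjusted difference is 0.625×0.42 − 0.38 = −0.118; in the second it is 0.625×0.44 − 0.36 = −0.085. Power is 64% and 39% unadjusted, 84% and 87% adjusted.

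**5. What adjustment cannot reach.** If risk differs between periods for unrecorded reasons, by 5 points over a base of 20% to 40%, the test rejects in 15% to 19% of trials with no treatment effect (both directions). For 10 points it rejects in 45% to 56%.

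**6. Open choice of outcome.** With k independent tests at 0.05 the chance of at least one false positive is 1 − 0.95^k: 9.75% for k = 2 and 14.3% for k = 3. Independence is assumed; positively correlated outcomes generally give less.

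**7. Duration, if reported.** Suppose incidence falls from 40% to 30% and control episodes last 3 or 9 days equally often, so the control mean among cases is 6.0. If only short episodes are prevented, the mean among gum arabic cases is (0.1×3 + 0.2×9)/0.3 = 7.0 days, and a cases-only comparison calls gum arabic worse in about 44% of runs, although nobody was harmed. This is a reason to define duration in all patients.

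**The case against.** Much of the case on the other side stands.

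- **The t-test.** A reader might infer that a t-test was misapplied to yes/no data. The documents do not show that: the sentence on suitable analysis leaves room for a test of proportions, and the section also speaks of analysing frequencies. What stands is that no other test, outcome or covariate is named.
- **Number of outcomes.** A reader might count every field as an outcome, reach seven and quote a false-positive risk of about 30%. Soreness, erythema and ulcers are parts of one assessment and are asked only after a 'yes', and nothing says that each was tested. Two or three outcomes is the fair count.
- **Duration.** No section says that duration was compared among cases only, or at all. Step 7 is a caution for reporting.
- **Separate periods.** These are inferred from one sentence; no dates per group are given. The wording supports little else, but the inference should be labelled as one.
- **Eligibility.** Excluding recent chemotherapy or radiotherapy, existing mucositis or periodontitis, and systemic disease removes some imbalance. Cancer type, stage and regimen remain open.
- **Limits of a model.** If period coincides with group, no covariate can separate them. Entering every recorded item is also unwise: with 166 per group, one binary factor and skewed covariates of 8, 6 and 4 levels (assumed), a logistic coefficient diverged in 35% to 44% of runs. Where the model fitted, error and power were unaffected.

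**Conclusion.** The concern holds. The plan's only named comparison is unadjusted, in a study with no described randomisation and groups apparently recruited in turn, although baseline data were collected. Under the assumed imbalances of 45% v 55% to 40% v 60%, a false benefit is called in about 5% to 32% of trials, against about 2.5% with adjustment for the recorded factor; the reverse imbalance produces false harm just as readily. These figures show what the mechanism can do. They do not show that bias occurred here, which way it would run or how large it was, and the documents do not support a claim that the result is wrong.

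The unnamed main outcome is a lesser defect, worth at most about 10% to 14% for two or three independent tests. The sponsor should correct both; the correction is cheap but only partial.

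**What to change.** - **Main outcome.** Any oral mucositis within six weeks, defined only as a 'yes' to the weekly occurrence question at any contact. It matches the prevention objective and is asked every time, whereas the summarised questions omit ability to eat. Label the choice post hoc: recruitment and follow-up stopped by August 2016 and the document is dated 15/11/2017.
- **Estimate.** Risk difference and risk ratio, gum arabic versus control, with 95% CI, from a logistic model with standardised risks. Show the unadjusted figures alongside.
- **Covariates.** A short list of recorded day-one characteristics, chosen without looking at outcome by group, plus the planned cycle interval at the first cycle if recorded. This interval also governs how often patients are seen in person. Collapse sparse categories.
- **Duration, if reported.** Days with mucositis in all patients (zero if none), counted to the end of week six for unresolved episodes, adjusted for the same covariates.
- **Supportive.** WHO score and individual signs.
- **Limits to state.** Adjustment cannot separate recruitment period from group, remove unrecorded confounding or the selection of the 332 completers, or restore prespecified error control. Causal wording should be limited to match.

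The cost is a small amount of analysis, and supportive outcomes lose stand-alone significance claims. The documents do not list the baseline items, so adjustment is confined to what exists. In the balanced example (40% v 25%, one binary factor, stratum standardisation) adjustment loses no power: 85% to 88% against 84%. Incidence can be the weaker outcome, for instance 84% v 96% for a mean score if gum arabic cases are also milder (assumed grade mix).

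### The Student t-test is the only test named for means, and nothing in the plan secures equal group sizes or equal spreads; Welch's form is safer at almost no cost

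*Combined protocol and SAP*

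**What the plan says.** The Statistical analysis section states: "Student t-test was used to assess the statistical significance of the difference between means of the two groups". No other test is named. The threshold is given as "P. values equal or less than 0.05 was considered significant", with no statement of sidedness. On intervals it says "All numeric variables were expressed at 95% confidence intervals". That sentence concerns numeric variables in general and does not mention the between-group difference. It also says that "suitable analysis was done according to the type of data obtained for each parameter". Pooled variance, equal variances and Welch's test are not mentioned.

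On group sizes, the only count is a total: "The data of 332 patients who completed this study were documented and reviewed to give a qualitative analysis of the frequencies". The section on cessation of trial therapy says that "there was a period of three weeks the new recruitment was suspended to separate study group from control group", and "No stop for recruiting the participants to study group until the planned number was completed". The planned number itself is not given. The section on modification of the preparation reports that frequent use and viscosity were features "which lead to withdrawn some patients after were enrolled in this study", again without a number.

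**The concern.** The pooled t-test estimates one common variance. It is sound when the groups are of equal size, or when they have equal spread. The plan secures neither.

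- **Sizes.** No ratio or randomisation is stated, the groups were filled separately, and the withdrawals described relate to a product that only the study group took. The 332 completers need not split evenly.
- **Spreads.** If the product prevents mucositis, a measure such as days affected, which cannot fall below zero, would usually lose spread as its mean falls. Groups recruited separately may also differ in case mix.

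When both differ, the direction of the error depends on which group is larger. If the smaller group is the more variable, the pooled interval is too short and p-values are too small. If the larger group is the more variable, the interval is too wide and p-values are too large.

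**Working it through.** The plan gives no SD, effect size, power or per-group n, so it has no figure of its own to reproduce.

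**Inputs from the document:** 332 completers, significance level 0.05 (two-sided assumed), 95% intervals. **Assumed:** the split, the SD ratio, the incidences, and a duration of 8 days (SD 4) in affected patients with zero days in the others. The questionnaire asks for start and end days, but the plan never defines days with mucositis as an analysed mean.

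**1. Spread of the illustrative outcome.** With incidence p, variance = p(16 + 64) − (8p)².
- 40%: 32 − 10.24 = 21.76, SD 4.7
- 25%: 20 − 4 = 16.00, SD 4.0
- 10%: 8 − 0.64 = 7.36, SD 2.7

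**2. Ratio of pooled to true standard error.** Pooled variance = [(n₁−1)s₁² + (n₂−1)s₂²]/(N−2), multiplied by (1/n₁ + 1/n₂). True variance = s₁²/n₁ + s₂²/n₂. With k = √(pooled/true), large-sample coverage is 2Φ(1.96k) − 1.

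| Study v control incidence | Study/control n | True variance | Pooled variance | k | Coverage of pooled interval |
|---|---|---|---|---|---|
| 25% v 40% | 221/111 | 0.2684 | 0.2425 | 0.951 | 93.7% |
| 25% v 40% | 111/221 | 0.2426 | 0.2685 | 1.052 | 96.1% |
| 10% v 40% | 221/111 | 0.2293 | 0.1646 | 0.847 | 90.3% |
| 10% v 40% | 111/221 | 0.1648 | 0.2295 | 1.180 | 97.9% |

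Simulation (gamma durations, zeros for unaffected patients) agrees to within a few tenths of a point. Welch's interval covers about 95% in all four rows. At 166/166, k = 1 and pooled coverage is 95.0%.

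**3. Power at 25% v 40%.** The difference in means is 8 × 0.15 = 1.2 days, and power ≈ Φ(1.2/SE − 1.96k), with k = 1 for Welch.
- 111 study, 221 control: SE = √0.2426 = 0.4926. Pooled Φ(2.436 − 2.062) = 64.6%; Welch Φ(2.436 − 1.96) = 68.3%.
- 221 study, 111 control: SE = √0.2684 = 0.5181. Pooled Φ(2.316 − 1.863) = 67.5%; Welch Φ(2.316 − 1.96) = 63.9%. Here the pooled test looks stronger only because its standard error is too small.

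At 10% v 40% both tests have power of about 99.9% or more.

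**4. Type I error** (simulated normal data, N = 332). With equal SDs the pooled test gives 5.0% to 5.1% at every split tried. At 166/166 it gives 5.0% at SD ratios from 1 to 3. It departs from 5% when the means are equal but both sizes and SDs differ:

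| Split | SD ratio | Smaller group more variable | Larger group more variable |
|---|---|---|---|
| 132/200 | 1.5 | 7.0% | 3.4% |
| 111/221 | 1.5 | 8.5% | 2.6% |
| 111/221 | 2 | 10.9% | 1.7% |

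Welch gives 4.9% to 5.1% throughout.

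**5. Cost of Welch when variances are equal.** Power is 79.8% for both tests at 166/166, 79.7% pooled v 79.5% Welch at 221/111, and 79.8% v 79.5% at 249/83.

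**The case against.** The strongest reply is that no distortion is shown. The split and the SDs are not in the document, and a planned number for the study group was reached, which weakens the inference from withdrawals to unequal groups. That stands. It does not establish a 1:1 split, but it means that harm is possible and not demonstrated.

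Several stronger readings are tempting:

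- **That the false-positive rate is 7% to 11%.** A reader might infer this from the second table above. The plan does not support it. If spreads differ only because the product works, then an ineffective product leaves both groups with the same distribution and the pooled test keeps its 5%. Those rates need a spread difference from another source, such as case mix.
- **That a real preventive effect would probably be missed.** In the illustration the loss is under 4 points at 25% v 40% and negligible at 10% v 40%.
- **That the plan commits to pooled variance.** This is a reading of the test's name. The general allowance for an analysis suited to the data type leaves some room, although the test then named for means is Student's. Likewise, the interval sentence does not say how an interval for the difference was formed.
- **That the main comparison is affected.** Mucositis is also recorded as weekly yes/no occurrence and on the WHO scale, so the t-test may not carry the prevention question.

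**Conclusion.** The point holds as a low-cost improvement. The only test named for means is, by convention, one that relies on equal sizes or equal spreads, and the plan documents neither. Under the assumed 2:1 split, coverage of a nominal 95% interval moves by about one point in either direction for a moderate effect (25% v 40%). For a fourfold reduction (10% v 40%) it falls by about five points or rises by about three. With equal groups or equal SDs nothing is lost. Because neither quantity is in the document, the actual error, if any, cannot be stated.

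The point concerns the variance formula only. It does not bear on confounding between separately recruited groups, on the handling of the yes/no and graded outcomes, or on the restriction to completers. Those matters are larger, and Welch's test would not resolve them.

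**What to change.** Compare group means with Welch's t-test (equal variances not assumed) and give its 95% confidence interval for the difference. Do not run a preliminary test of variances. Report n and SD for each group so that a reader can see whether the choice mattered. If a regression model is used for the comparison, use robust standard errors for the same reason.

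The plan is dated November 2017, describes its analysis in the past tense, and records that recruitment and follow-up stopped by August 2016. This is therefore a re-run of the mean comparisons, to be labelled as a change from the stated analysis. The report should also say which variance form was used before.

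No new data are needed. If the variances are in fact equal, the loss is at most about 0.3 points of power in the splits tried.
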